17. DATA HANDLING AND RECORDKEEPING

17.1. Inspection of Records

Sage Therapeutics or its representative(s) will be allowed to conduct visits at the investigation site and/or supporting facilities for the purpose of monitoring any aspect of the study. The investigator agrees to allow the monitor to inspect the facility, drug storage area, drug accountability records, participant medical records and study source documents, and other records relative to study conduct.

Inspection of the study by a Regulatory Authority may occur at any time. The investigator must agree to the inspection of study-related records and source documents by the Regulatory Authority representative(s).

17.2. Retention of Records

[figure not shown]
The principal investigator must maintain all documentation relating to the study for the period outlined in the site contract, or for a period of 2 years after the last marketing application approval, and until there are no pending or contemplated marketing applications in an ICH region or at least 2 years have elapsed since the formal discontinuation of clinical development of the IP. Sage is responsible to inform the investigator/institution as to when study documents no longer need to be retained.

18. PUBLICATION POLICY

All information concerning SAGE-324 is considered confidential and shall remain the sole property of Sage Therapeutics. The investigator agrees to use this information only in conducting the study and shall not use it for any other purposes without written approval from Sage Therapeutics. No publication or disclosure of study results will be permitted except as specified in a separate, written, agreement between Sage Therapeutics and the investigator.

eSignature Approval Task	[REDACTED]
	08-Nov-2023 16:09:27 GMT+0000
eSignature Approval Task	[REDACTED]
	08-Nov-2023 20:35:11 GMT+0000

Signature Page for VV-CLIN-003088 v1.0

Protocol 324-ETD-303, Amendment 3

Summary of Changes

Date of Amendment: 02 November 2023

An Open-label Study of the Long-term Safety and Tolerability of SAGE-324 in Participants with Essential Tremor

Protocol Amendment 3 reflects the following changes:

- The Sponsor Contact has changed from:

Phone: [REDACTED]

E-mail: [REDACTED]

to:

Phone: [REDACTED]

E-mail: [REDACTED]

Note: As per Administrative Letter #6 dated September 25, 2023, the Sponsor Contact changed to [REDACTED]. In Protocol Amendment 3, the Sponsor Contact has been updated to [REDACTED].

- The Sponsor Medical Monitor and Study Physician have changed from:

[REDACTED] MD, MSc

Phone: [REDACTED]

E-mail: [REDACTED]

to:

[REDACTED] MD

Phone: [REDACTED]

Email: [REDACTED]

- Section 2 Schedule of Assessments: As per Administrative Letter #4 dated May 11, 2023, added collection of alcohol, nicotine products and diet to ensure alignment with Inclusion Criteria #9, #10, and Exclusion Criterion #14, respectively.
- Section 9.2.3 Prohibited Medications: As per Administrative Letter #5 dated July 17, 2023, the following was added for clarity:
 - Any estrogen-containing products that are widely absorbed into the systemic circulation (eg, oral, transdermal, transvaginal, etc.), used for any indication, are prohibited from Day -14 and during the study.
- Section 2 Synopsis, Section 7.1 Overall Study Design, and Section 9.2.3 Other Restrictions:

- Updated guidance regarding gaining experience with how the study drug may affect the participant before engaging in potentially hazardous activities requiring mental alertness, such as driving.
- Section 12.4 Overdose was changed to Section 12.4 Special Considerations, with new language for “abuse” and “misuse” to align with the Regulation (EU) No 536/2014 Of the European Parliament and Of The Council.
- The Sponsor Approval page was deleted to align with current Sage process and template.
- Minor formatting changes

Protocol 324-ETD-303, Amendment 2

Date of Amendment: 16 November 2022

**AN OPEN-LABEL STUDY OF THE LONG-TERM SAFETY AND TOLERABILITY OF
SAGE-324 IN PARTICIPANTS WITH ESSENTIAL TREMOR**

Rationale for Protocol Amendment

The main purpose for this protocol amendment is to update eligibility criteria.

Changes to the protocol include:

- Permit alcohol consumption with restrictions on amount and timing with scheduled study visits (new Inclusion Criterion 9 [Synopsis and Section 8.1] and Section 9.2.4)
- Permit current use of nicotine products at prestudy levels (new Inclusion Criterion 10 [Synopsis and Section 8.1] and Section 9.2.4)
- Exclude participants with nicotine use disorder (Exclusion Criterion 6 [Synopsis and Section 8.2] and Section 9.2.4)
- Remove alcohol and cotinine screening (Table 2 and Section 12.1.6.1)
- Clarify that participants have completed the planned End of Treatment Visit and were not early terminated during the planned Treatment Period in another SAGE-324 study (Inclusion Criterion 5 [Synopsis and Section 8.1] and study description [Synopsis and Section 7.1])
- Include creatine kinase, myoglobin, HgA1c, and blood alcohol level in clinical laboratory assessments (Schedules of Assessments and Section 12.1.6)
- Clarify that participants should not engage in potentially hazardous activities requiring mental activities until any sleepiness and sedative effects of IP have dissipated (Synopsis and Section 7.1)
- Prohibit use of estrogen-containing contraceptives that are widely absorbed into the circulatory system as an acceptable forms of highly effective contraception methods for female participants of childbearing potential or for female partners of male participants who are of childbearing potential (Section 9.2.5)
- Define End of Study(EOS) (new Section 7.6)
- Define procedures for protection of participant data (new Section 16.4)
- Update safety reporting requirements (new Section 12.2.4, Section 12.3, Section 12.4, Section 15, and Section 16.4)

Updates to organization, formatting, descriptions of procedures, and Sage personnel have also been made.

Protocol 324-ETD-303, Amendment 1

Date of Amendment: 28 June 2022

**AN OPEN-LABEL STUDY OF THE LONG-TERM SAFETY AND TOLERABILITY OF
SAGE-324 IN PARTICIPANTS WITH ESSENTIAL TREMOR**

Rationale for Protocol Amendment

[REDACTED]

Additional changes to the protocol include:

- Update SAE reporting to include both CRO and Sage personnel following DSPV guidance (Table 1 and Section 12.2.5)
- Update ECG assessment from triplicate to single readings at all timepoints (Schedule of Events and Section 12.1.5)
- Add that, at the discretion of the investigator, clinical laboratory assessments from a completed SAGE-324 study may be used to determine eligibility for this study if taken within 28 days of Day 1 (Section 7.1)
- [REDACTED]
- Update objectives (Section 6.0)
 - Update Primary objective to: “To evaluate the long-term safety and tolerability of SAGE-324”
 - Update Secondary safety objective to: “To evaluate the long-term effect of SAGE-324 on other safety parameters”
- [REDACTED]
- Clarify eligibility requirements with minor textual changes to inclusion criterion 5 and exclusion criteria 3, 6, and 9 (Sections 8.1 and 8.2)
- Clarify that 20-item Physician’s Withdrawal Checklist scores are not compared to baseline and that this assessment will be used to evaluate potential withdrawal symptoms (Section 13.7)
- Include use of breathalyzer for determination of alcohol use (Section 12.1.6.1)
- Clarify that participants that do not complete End of Study Visit will be considered lost to follow-up (Section 8.4.2)

Relevant changes in the protocol are also included in Section 2 (Synopsis).

Updates to organization, formatting, and Sage personnel have also been made.

1. LIST OF ABBREVIATIONS

The following abbreviations and specialist terms are used in this statistical analysis plan (SAP).

Table 1: Abbreviations and Specialist Terms

Abbreviation	Definition
AE	adverse event
[REDACTED]	[REDACTED]
BMI	body mass index
COVID-19	Coronavirus disease 2019
C-SSRS	Columbia-Suicide Severity Rating Scale
ECG	electrocardiogram
eCRF	electronic case report form
EOS	End of Study
EOT	End of Treatment
ESS	Epworth Sleepiness Scale
ET	essential tremor
IP	investigational product
MedDRA	Medical Dictionary for Regulatory Activities
[REDACTED]	[REDACTED]
[REDACTED]	[REDACTED]
PWC-20	20-item Physician Withdrawal Checklist
QTcF	QT corrected according to Fridericia's formula
SAE	serious adverse event
SAP	statistical analysis plan
SD	standard deviation
SOC	System Organ Class
TEAE	treatment-emergent adverse event
[REDACTED]	[REDACTED]
WHO-DD	World Health Organization Drug Dictionary

2. INTRODUCTION

This statistical analysis plan (SAP) is for the final analysis of Study 324-ETD-303 and is based on the approved clinical study protocol dated 02 Nov 2023, Version 4.0.

This SAP addresses the objectives of the study and describes the planned statistical analyses and data presentations. All analyses and data presentations will be generated using SAS® Version 9.4 or higher software (SAS Institute, Cary, North Carolina, USA). This SAP will be finalized and approved before the clinical database lock. Any changes made to the SAP after the clinical database lock has occurred will be documented and discussed in the clinical study report for this study.

3. STUDY OBJECTIVES

3.1. Primary Objective

The primary objective of this study is to assess the long-term safety and tolerability of SAGE-324.

3.2. Secondary Objective

The secondary objective of this study is to assess the long-term effect of SAGE-324 on other safety parameters.

[REDACTED]

4. STUDY ENDPOINTS

4.1. Primary Endpoint

The primary endpoint of this study is the incidence of TEAEs.

4.2. Secondary Endpoints

The secondary endpoint(s) of this study are:

- The change from baseline in vital sign parameters
- The change from baseline in electrocardiogram (ECG) parameters
- The change from baseline in clinical laboratory parameters (eg, serum chemistry, hematology, coagulation, and urinalysis)
- Change from baseline in Epworth Sleepiness Scale (ESS) responses
- Physician Withdrawal Checklist (PWC-20) responses and total score
- Change from baseline in Columbia-Suicide Severity Rating Scale (C-SSRS) responses

5. STUDY DESIGN

5.1. Overall Design

This study is an open-label study to evaluate the long-term safety and tolerability of SAGE-324 in participants with Essential Tremor (ET) who have completed the planned End of Treatment (EOT) Visit and who were not early terminated during the planned Treatment Period in another SAGE-324 study. This study includes a Screening Period of up to 28 days, a Treatment Period with weekly outpatient visits for the first 8 weeks, outpatient visits on Weeks 10, 12, 16, 20, and 24, and quarterly outpatient visits thereafter to the end of dosing, and a 14-day Follow-up Period. See the Schedule of Assessments ([Appendix A](#)) for the full list of study assessments and timings. The study is schematically presented in [Figure 1](#).

Participants who have provided informed consent will undergo screening assessments up to 28 days prior to the planned day of dosing. Eligible participants will complete additional eligibility and baseline assessments.

[figure not shown]
Starting on Day 1, participants will self-administer on an outpatient basis a single dose of SAGE-324 once daily in the evening before bed, with a snack if bedtime is not within 2 hours of the evening meal. The dosing will start at 15 mg, and according to the dose escalation schedule provided in Figure 1 below, will be escalated to 60 mg starting on Day 43. If a participant experiences adverse events (AE) at any time during the Treatment Period that are considered by the investigator to be related to the investigational product (IP) and not tolerable, the investigator may reduce the dose of IP in 15 mg decrements, including during the initial dose escalation period. Administration of IP will be interrupted for 3 to 8 days before the initiation of the reduced dose.

During the Treatment Period, participants will return to the study center for safety, tolerability [REDACTED] as specified in [Appendix A](#). In addition, safety phone call study visits will be conducted as deemed appropriate by the investigator to review the current status of the participant. Participants will be trained in the use of software applications and devices necessary to complete questionnaires and/or self-rated study assessments.

The Treatment Period will continue for as long as the participant continues to self-administer SAGE-324 or until marketing authorization, projected to be up to approximately 5 years.

Follow-up visits will be conducted on an outpatient basis when participants have completed the Treatment Period. Participants will continue to complete questionnaires as indicated in [Appendix A](#) and will return to the clinic 3 (± 3) days after the last dose of SAGE-324 for safety, tolerability [REDACTED] at the End of Treatment (EOT) Visit.

Participants will return to the study center for an End of Study (EOS) Visit, 14 (± 3) days after the last dose of SAGE-324.

Figure 1: Study Design

5.2. Sample Size and Power

The planned sample size is approximately 750 participants to be dosed and complete the study to contribute exposures to the safety database for SAGE-324 in accordance with ICH E1A guidelines.

[REDACTED]

5.3. Randomization

This is an open label study, hence no randomization is applicable.

5.4. Blinding and Unblinding

This is an open label study, hence no blinding is applicable.

6. MODIFICATIONS

6.1. Modifications from the Approved Clinical Study Protocol

There are no modifications in analysis specified in the clinical study protocol (version 4.0, dated 02 Nov 2023).

6.2. Modifications from the Approved Statistical Analysis Plan

This is the first version of the SAP for the final analysis.

6.3. Modifications from the Approved DMC Charter

Not Applicable.

7. ANALYSIS SETS

7.1. All Participants Set

The All Participants Set will include all participants who have given written informed consent.

7.2. Safety Set

The Safety Set is defined as all participants who administered at least one dose of SAGE-324.

[REDACTED]

8. STATISTICAL ANALYSIS

8.1. General Considerations

All participant data, including those that are derived, that support the tables and figures will be presented in the participant data listings. Some data may be presented only in participant data listings, some may be presented with a corresponding table or figure; these will be indicated in relevant sections below.

For all safety [REDACTED] analyses where applicable, baseline is defined as the last non-missing measurement prior to the first dose of IP. For scores that are made up of item scores, all item scores must come from the same visit to be considered as baseline for the overall score.

Continuous endpoints will be summarized with n, mean, standard deviation (SD), median, first and third quartiles (Q1, Q3), minimum (min), and maximum (max). The minimum and maximum will be reported with the same number of decimal places as the source (raw) data. Mean and median will be reported to 1 decimal place more than the source (raw) data and standard deviation will be reported to 2 decimal places more than the source (raw) data. Any values that require transformation to standard units (metric or SI) will be converted with the appropriate corresponding precision. In addition, change from baseline values will be calculated at each time point and summarized descriptively.

Categorical endpoints (eg, incidence of an adverse event) will be summarized using counts and percentages. Percentages will be presented to 1 decimal place unless otherwise specified.

Participants will be summarized according to treatment received. “By-visit” summaries are based on the last dose received before the specific evaluation. Adverse events summaries are based on the last dose received before the start of the AE. Note that it is possible for a participant to be counted under more than one dose in summaries. Since baseline is by definition before the first dose of IP, baseline values in listing will have no dose designation, and in summaries it will be presented under “Sage-324 Overall”. For displays for which no such date applies, e.g. demographics, disease history, etc., the presentation will not be by dose group, but will be by aggregate SAGE-324 group.

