7. INVESTIGATIONAL PLAN

7.1. Overall Study Design

This is an open-label study to evaluate the long-term safety and tolerability of SAGE-324 in participants with ET who have completed the planned End of Treatment (EOT) Visit and who were not early terminated during the planned Treatment Period in another SAGE-324 study.

The study design is presented in Figure 2.

Figure 2: Study Design

This study includes a Screening Period of up to 28 days, a Treatment Period with weekly outpatient visits for the first 8 weeks, outpatient visits on Weeks 10, 12, 16, 20, and 24, and quarterly outpatient visits thereafter to the end of dosing, and a 14-day Follow-up Period. After providing informed consent, participants will undergo screening assessments as outlined in [Table 2](#) to determine eligibility.

Screening Period:

The Screening Period begins with the signing of the informed consent form (ICF). Eligible participants will complete additional eligibility and baseline assessments, as specified in the Schedule of Assessments ([Table 2](#)).

At the discretion of the investigator, clinical laboratory assessments from a completed SAGE-324 study may be used to determine eligibility for this study if taken within 28 days of Day 1.

Open-label Treatment Period:

Starting on Day 1, participants will self-administer on an outpatient basis a single dose of SAGE-324 once daily in the evening before bed, with a snack if bedtime is not within 2 hours of the evening meal. Guidance on suitable snacks will be provided.

During the Treatment Period, participants will return to the study center for safety, tolerability, [REDACTED] as specified in [Table 2](#), [Table 3](#), and [Table 4](#). In addition, safety phone call study visits will be conducted as deemed appropriate by the investigator to review the current status of the participant. Participants will be trained on the use of software applications and devices necessary to complete questionnaires and/or self-rated study assessments.

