12.1.4. Vital Signs

Vital signs comprise heart rate, respiratory rate, temperature, and blood pressure. Systolic and diastolic blood pressure are to be measured after the participant has been supine for at least 5 minutes prior to the measurement. Orthostatic blood pressure and heart rate will also be measured after the participant has been in the supine position for at least 5 minutes and then repeated approximately 1 and 3 minutes after standing.

On Day 1, supine and standing blood pressure and heart rate will be collected in triplicate at least 15 minutes apart, measured after the participant has been in the supine position for at least 5 minutes and then repeated 1 minute and 3 minutes after standing. Respiratory rate and temperature are collected once on Day 1.

Any abnormality in vital signs will be interpreted by an investigator as abnormal, NCS or abnormal, CS in source documents.

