13.3. General Considerations

For the purpose of all safety, tolerability [REDACTED] where applicable, baseline is defined as the last measurement prior to the start of IP administration.

Continuous endpoints will be summarized with number (n), mean, standard deviation, median, minimum, and maximum. In addition, change from baseline values will be calculated at each time point and summarized descriptively. For categorical endpoints, descriptive summaries will include counts and percentages.

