8.4. Safety Analysis

Safety and tolerability of SAGE-324 will be assessed based on TEAEs, changes from baseline in clinical laboratory evaluations, 12-lead ECGs, and vital signs, C-SSRS, PWC-20, and ESS. Safety data will be listed by participant.

For safety summary tables, the safety endpoints evaluated at scheduled visits are taken as done and nominal visit will be summarized as scheduled visits. For multiple values from the specific visit window, the choice of the visit record will be following the same rule as described in [Section 8.3.2](#).

All safety summaries will be prepared by dose level and overall for the Safety Set. See [Table 4](#) for details on how safety endpoints will be presented.

Table 4: Presentation of Safety Endpoints

Safety Evaluation	Incidence	Raw Value	Change from Baseline	Abnormality	Derived PCS values
TEAEs	X	*			
Vital Signs		X, *	X		X, *
12-lead ECG		X, *	X	X, *	X, * (QTcF only)
Safety Labs (Chemistry, Hematology, Urinalysis)		X, *	X	X, *	X, *
ESS	X	*	X		
PWC-20	X	*			
C-SSRS	X	*	X		

X = Safety Assessment will be summarized in tables
 * = Safety Assessment will be presented in individual participant data listings
 Note: PCS = Potentially Clinically Significant.

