8.4.3. Electrocardiogram

All by-visit ECG summary tables will present results for Safety Set participants overall, and also by dose level received prior to the evaluation. For summarization of incidence any time post-baseline, participant data will be summarized according to the last dose received when a particular criterion was met (thus, a participant may contribute data under more than one dose if a criterion was met post-baseline while taking different doses). Last value on treatment and last value on study will be summarized under the dose level last received.

The average of any multiple values collected at one visit will be used for summarization of continuous variables, including baseline ECG values. For each ECG measurement (heart rate and PR, QRS, QT, and QTcF intervals), the observed value at each scheduled visit and change from baseline at each scheduled visit will be provided. This summary will also include last values on treatment and on study. Last value on treatment is defined as the last post-baseline value between first dose of IP (exclusive) and up to last dose of IP + 1 day (inclusive). Last value on study is defined as the last post-baseline value after the first dose of IP.

In addition, the number and percentage of participants with PCS and potentially clinically significant change (PCSC) values will be summarized by scheduled timepoint and for any time post-baseline, including last value on treatment and last value on study. Individual values of QTcF will be used for PCS determination rather than the average of multiple values collected at one visit. Potentially clinically significant values will be identified for ECG parameters as outlined in [Table 9](#).

A shift table of overall ECG interpretation from baseline to scheduled post-baseline visits will be presented for the following categories: 'Normal', 'Abnormal, Not Clinically Significant', and 'Abnormal, Clinically Significant'. The shift table will be presented by visit – overall and by dose level.

Clinically significant abnormal findings will be reported as adverse events. The average of any multiple values collected at one visit of each parameter will be included in the data listing.

Table 9: Potentially Clinically Significant Values for QTcF

Units	Criteria for PCS Values (Observed Values)		Criteria for PCSC Values (Change from Baseline)	
	High	Low	Increase	Decrease

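### Day 1 blood pressure and heart rate are taken in triplicate, but the only visible baseline rule uses the last reading; averaging the replicates would cut noise in the changes and false blood pressure flags at no data cost.

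*SAP*

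**What the plan says.** **Collection.** Protocol 12.1.4, repeated in footnote b of Table 2 and in SAP Appendix A, states: "On Day 1, supine and standing blood pressure and heart rate will be collected in triplicate at least 15 minutes apart". Each set has a supine reading and standing readings at 1 and 3 minutes. The other vital signs are not replicated: "Respiratory rate and temperature are collected once on Day 1". No later visit calls for triplicates. Dosing is "a single dose of SAGE-324 once daily in the evening before bed", so the Day 1 clinic readings should be pre-dose.

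**Baseline.** SAP 8.1 states, for all safety analyses where applicable: "baseline is defined as the last non-missing measurement prior to the first dose of IP". Protocol 13.3 agrees: "baseline is defined as the last measurement prior to the start of IP administration".

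**Replicates.** SAP 8.4.4 (Vital Signs) has no rule for them. SAP 8.4.3 has one for ECG: "The average of any multiple values collected at one visit will be used for summarization of continuous variables, including baseline ECG values". For several values within a visit window, SAP 8.4 says that "the choice of the visit record will be following the same rule as described in" Section 8.3.2, which is not in the public text.

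**Use of baseline.** Change from baseline in vital signs is a secondary endpoint (SAP 4.2). SAP Table 10 flags a change in systolic pressure of at least 30 mmHg, and in diastolic pressure of at least 20 mmHg, in either direction. It has no change criterion for heart rate.

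**The concern.** The one set of vital signs with planned baseline replicates has no stated way of combining them, and the general rule points to a single reading. Elsewhere the SAP departs from 8.1 when it wants something different: ECG baseline is averaged (8.4.3), and C-SSRS baseline is the worst pre-dose assessment (8.4.6). Section 8.4.4 contains no such departure.

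Any error in that single reading enters every later change for the same participant. A reading that happens to be low makes increases look larger at all visits, and a high one does the same for decreases. The study has one arm, so no control group shows how many blood pressure flags would arise from measurement variation alone.

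**Working it through.** **Plan's own figure.** There is none to reproduce. The documents give no vital-sign SD, no within-visit correlation and no expected flag rate. The sample size of about 750 is used here only to scale counts.

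**Inputs from the documents.** Three Day 1 readings (protocol 12.1.4); no replication planned at later visits; limits of 30 and 20 mmHg (SAP Table 10); 13 scheduled post-baseline visits to Week 24, being 8 weekly visits (Days 8 to 57) plus Weeks 10, 12, 16, 20 and 24.

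**Assumed inputs.** A reading is the person's mean, plus a visit deviation (SD b), plus a within-visit deviation (SD e). All are normal and independent, with no true change. The within-visit share is w = e²/(b² + e²).

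**Formulas.**
- Last reading as baseline: Var(change) = 2(b² + e²).
- Mean of three as baseline: Var(change) = (b² + e²) + (b² + e²/3) = 2b² + (4/3)e².
- Proportional reduction = (2/3)e² / [2(b² + e²)] = w/3. It cannot exceed one third. At that ceiling (w = 1) the SD of change under the last-reading rule is √1.5 = 1.225 times as large.

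**Worked case, systolic b = 8, e = 6 mmHg.** Last reading: 2(64 + 36) = 200, SD 14.14. Mean of three: 128 + 48 = 176, SD 13.27. The reduction is 24/200 = 12%. The two-sided tail at 30 mmHg is 3.4% (z = 2.12) against 2.4% (z = 2.26) at one visit.

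**Range.** The any-visit figures are simulated, with all 13 changes sharing one baseline and both directions pooled. Counts come from unrounded percentages.

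| b / e (mmHg) | w | Variance reduction | One visit: last vs mean | Any of 13 visits: last vs mean | Fewer flagged per 750 |
|---|---|---|---|---|---|
| 10 / 3 | 0.08 | 2.8% | 4.2% vs 3.9% | 29.2% vs 28.2% | about 8 |
| 9 / 4 | 0.16 | 5.5% | 3.1% vs 2.7% | 23.0% vs 21.0% | about 14 |
| 7 / 3 | 0.16 | 5.2% | 0.5% vs 0.4% | 5.1% vs 4.2% | about 6 |
| 6 / 4 | 0.31 | 10.3% | 0.3% vs 0.2% | 3.2% vs 2.1% | about 9 |
| 8 / 6 | 0.36 | 12.0% | 3.4% vs 2.4% | 24.6% vs 20.1% | about 34 |
| 7 / 7 | 0.50 | 16.7% | 3.2% vs 1.9% | 23.5% vs 17.2% | about 47 |
| 6 / 8 | 0.64 | 21.3% | 3.4% vs 1.7% | 24.5% vs 16.1% | about 63 |

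**Diastolic, one visit, increases only.** With an assumed single-reading SD of 7 mmHg, the last-reading rule gives 2.17% at or above 20 mmHg. The mean rule gives 1.83%, 1.50% and 1.19% for w = 0.2, 0.4 and 0.6. At w = 0.4 that is 16.3 against 11.2 per 750.

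**Not affected.** Respiratory rate and temperature (one reading each), the observed-value limits, and the supine-minus-standing criteria, which do not use baseline.

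**The case against.** A reader might infer that two of the three readings are certainly thrown away. The documents do not establish that. SAP 8.4 sends multiple values in a visit window to Section 8.3.2, which cannot be read. Its description suggests selecting a record rather than averaging, but that is inference from a phrase. The general rule in 8.1 also covers ECG, where 8.4.3 averages, so a measurement in this SAP need not mean one replicate. This objection stands and lowers confidence. What remains is that no visible text says how the triplicates form the baseline, and the visible rule points to the last one.

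A reader might also infer that every vital-sign change is affected, or that mean changes are biased. Neither follows. Only blood pressure, heart rate and the derived pulse pressure have replicates to lose, and only systolic and diastolic pressure have change flags. Mean change is unbiased if the readings are exchangeable. If they drift over the session, the two rules would give different means, and the documents offer nothing on that.

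The size is also open to challenge. The last three table rows alone would suggest 34 to 63 participants, but they all put at least 36% of the variance within visit. Smaller shares or smaller SDs give 6 to 14. Table 10 lists increases and decreases separately, whereas the counts pool them, and full attendance is assumed. Most false flags would remain after averaging, because post-baseline readings are single and visits are many.

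Finally, the summaries are descriptive, the primary endpoint is TEAE incidence, and vital signs that the investigator judges clinically significant are recorded as adverse events regardless of baseline. The protocol states no purpose for the triplicates, and ECG averaging still has a use because protocol 12.1.5 allows a confirmatory repeat. These points limit the consequence but give no reason to prefer one reading to the mean of three.

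**Conclusion.** The point holds as a precision problem of uncertain size, with moderate confidence. On the visible text, baseline for blood pressure and heart rate is the last pre-dose reading although three are collected. Relative to the mean of three, that adds (2/3)e² to the variance of every change in these parameters and raises the systolic and diastolic change counts when there is no true change.

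Under the assumed systolic SDs, averaging would lower the variance of change by about 3% to 21%, and about 6 to 63 fewer of 750 participants would have at least one false systolic flag over 13 visits. These figures rest on SDs that are not in the documents, normal readings, no true change, full attendance and both directions pooled. If Section 8.3.2 already averages the replicates, the analysis loses nothing and only the wording of 8.1 needs to agree with it.

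**What to change.** Add to SAP 8.4.4:

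*For blood pressure and heart rate, baseline is the mean of the non-missing Day 1 pre-dose replicate readings, averaged separately for supine, 1-minute standing and 3-minute standing. If no Day 1 pre-dose reading is available, the last pre-dose value is used. Each post-baseline reading is compared with the baseline for the same position and time after standing.*

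Use this baseline for the change summaries and the change criteria in Table 10. The wording covers participants with only one or two of the three readings. It also closes a related gap: neither document says whether the 1-minute or the 3-minute reading is the standing baseline. Because protocol 13.3 specifies the last measurement, record the rule in SAP 6.1, which currently reports no modifications.

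The cost is a few lines of SAP text and minor programming. No new data are needed.
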